9.2 Comparable Methods

For the analysis of erlotinib, both LCMSMS and HPLC assays are available methodologies. LCMSMS is usually preferred over HPLC due to its improved sensitivity although both methods are standard for quantitative analysis of drug levels. For expression of tissue biomarkers the options of assessing message RNA or DNA levels exists in addition to gene product levels (protein expression). Our goal is to assess direct and indirect effects of erlotinib upon bladder urothelium and based on this goal and the convenience of examining protein expression from paraffin blocks or unstained slides, we have chosen protein expression (with the exception of let-7 which is microRNA expression). The increased sensitivity and ability to also examine cellular localization of protein expression has led us to use the multispectral analysis of the VECTRA system rather than standard qualitative expression of macro or micro array immunohistochemistry.

10. SPECIMEN MANAGEMENT

10.1 Laboratories

The University of Wisconsin Comprehensive Cancer Center's 3P Laboratory (Pharmacodynamics, Pharmacokinetics, Pharmacogenomics Lab) will serve as the central repository for all research specimens. The UWCCC 3P Laboratory will prepare sample kits for each subject enrolled on the study. Each site will receive one kit as they activate the study. The 3P lab will send additional kits to the sites as needed based on the rate of accrual. All tissue biomarkers will be done in the University of Wisconsin Translational Research in Pathology (TRIP) Laboratory under the direction of [name] (Study Pathologist).

10.2 Collection and Handling Procedures

10.2.1. Methods for drawing and processing the pharmacokinetics of blood:

At each pharmacokinetic time point draw one 3ml green top tube. Centrifuge the tube for 10 minutes to separate plasma. Divide the plasma into 2 cryovial tubes. Label the 2 cryovial tubes with the labels provided in the kit. Make sure to add the participant number, initials, date, and hour: minute of the pharmacokinetic blood draw to the labels. Freeze the cryovial tubes at -70°C , and save for transport to the UWCCC 3P Laboratory. The 3P Laboratory has purchased a software system to track samples.

10.2.2 Tissue Handling:

Biopsy tissues will be sent to Surgical Pathology for routine fixation, processing and embedding. Each site will provide tissue blocks of normal appearing bladder urothelium adjacent to tumor and tumor OR 10 unstained slides representing normal appearing bladder urothelium adjacent to tumor and 10 unstained slides representing tumor tissue (when available).

10.3 Shipping Instructions

10.3.1 Shipping to UWI

Once a patient has completed the study and all laboratory samples have been collected, ship the carton containing all of the samples for one patient to the address below. If multiple patients are completing the study, samples from multiple patients can be combined in one shipment.

3P Lab
[name]
[name]

Call the 3P Lab to inform them of a shipment [contact] or email the 3P lab mailing list [contact]

Use the express courier service indicated by the shipping label contained in the kit. Closely follow all special shipping instructions outlined in the kit instruction packet.

Ship only on Monday, Tuesday or Wednesday to ensure safe arrival during the week. Do not ship the day before a holiday.

Fill the styrofoam cooler with dry ice and put all of the blood samples into the cooler. Place the cooler into the shipping box in which you received the kit.

10.4 Tissue Banking

Biologic specimens collected during the conduct of each clinical trial that are not used during the course of the study will be considered deliverables under the contract and thus the property of the NCI. At study completion, NCI reserves the option to either retain or relinquish ownership of the unused biologic specimens. If NCI retains ownership of specimens, the Contractor shall collect, verify and transfer the requested biologic specimens from the site to a NCI-specified repository or laboratory at NCI's expense.

11. REPORTING ADVERSE EVENTS

DEFINITION: An adverse event (AE) is any untoward medical occurrence in a study participant. An AE does not necessarily have a causal relationship with the treatment or study participant. An AE can

therefore be any unfavorable and unintended sign (including an abnormal laboratory finding), symptom, or disease temporally associated with participation in a study, whether or not related to that participation. This includes all deaths that occur while a participant is on a study.

A list of adverse events that have occurred or might occur (Reported Adverse Events and Potential Risks) can be found in Section 6.2, Pharmaceutical Information as well as the Investigator Brochure.

11.1 Adverse Events

11.1.1 Reportable AEs

All AEs that occur after the informed consent is signed and baseline assessments are completed (including run-in) must be recorded on the AE CRC (paper and/or electronic) whether or not related to study agent.

11.1.2 AE Data Elements:

The following data elements are required for adverse event reporting.

- AE verbatim term
- System Organ Class (SOC)
- Common Terminology Criteria for Adverse Events v4.0 (CTCAE) AE term
- Event onset date and event ended date
- Severity grade
- Attribution to study agent (relatedness)
- Whether or not the event was reported as a serious adverse event (SAE)
- Whether or not the subject dropped due to the event
- Outcome of the event

11.1.3 Severity of AEs

11.1.3.1 Identify the AE using the NCI Common Terminology Criteria for Adverse Events (CTCAE) version 4.0. The CTCAE provides descriptive terminology and a grading scale for each adverse event listed. A copy of the CTCAE can be found at http://ctep.cancer.gov/protocolDevelopment/electronic_applications/ctc.htm

AEs will be assessed according to the CTCAE grade associated with the AE term. AEs that do not have a corresponding CTCAE term will be assessed according to the general guidelines for grading used in the CTCAE v4.0. as stated below.

CTCAE v4.0 general severity guidelines:

Grade	Severity	Description
1	Mild	Mild; asymptomatic or mild symptoms; clinical or diagnostic observations only; intervention not indicated.
2	Moderate	Moderate; minimal, local or noninvasive intervention indicated; limiting age-appropriate instrumental activities of daily living (ADL)*.
3	Severe	Severe or medically significant but not immediately life-threatening; hospitalization or prolongation of hospitalization indicated; disabling; limiting self-care ADL**.

Grade	Severity	Description
4	Life-threatening	Life-threatening consequences; urgent intervention indicated.
5	Fatal	Death related to AE.

ADL

*Instrumental ADL refers to preparing meals, shopping for groceries or clothes, using the telephone, managing money, etc.

**Self-care ADL refers to bathing, dressing and undressing, feeding self, using the toilet, taking medications, and not bedridden.

11.1.4 Assessment of relationship of AE to treatment

The possibility that the adverse event is related to study agent will be classified as one of the following: not related, unlikely, possible, probable, definite.

11.1.5 Follow-up of AEs

All AEs, including lab abnormalities that in the opinion of the investigator are clinically significant, will be followed according to good medical practices and documented as such.

11.2 Serious Adverse Events

11.2.1 DEFINITION: Fed. Reg. 75, Sept. 29, 2010 defines SAEs as those events, occurring at any dose, which meet any of the following criteria:

- Results in death
- Is life threatening (*Note: the term life-threatening refers to an event in which the patient was at risk of death at the time of the event; it does not refer to an event which hypothetically might have caused death if it were more severe*).
- Requires inpatient hospitalization or prolongation of existing hospitalization
- Results in persistent or significant incapacity or substantial disruption of the ability to conduct normal life functions
- Is a congenital abnormality/birth defect
- Important medical events that may not result in death, be life-threatening or require hospitalization may be considered serious when, based upon appropriate medical judgment, they may jeopardize the patient or subject and may require medical or surgical intervention to prevent one of the outcomes listed.

11.2.2 Reporting SAEs to DCP

11.2.2.1 The Lead Organization and all Participating Organizations will report SAEs on the DCP form found at http://prevention.cancer.gov/files/clinical-trials/SAE_form.doc.

11.2.2.2 Contact the DCP Medical Monitor by phone within 24 hours of knowledge of the event.

[name]
Prostate and Urologic Cancer Research Group
Division of Cancer Prevention, National Cancer Institute, NIH, DHHS
Shady Grove Campus
[name]
[name]
[contact]
[contact]

Include the following information when calling the Medical Monitor:

- Date and time of the SAE
- Date and time of the SAE report
- Name of reporter
- Call back phone number
- Affiliation/Institution conducting the study
- DCP protocol number
- Title of protocol
- Description of the SAE, including attribution to drug and expectedness

11.2.2.3 The Lead Organization and all Participating Organizations will FAX written SAE reports to the DCP Medical Monitor within 48 hours of learning of the event using the paper SAE form. The written SAE reports will also be Faxed [contact]) or emailed ([contact]) to DCP's Regulatory Contractor, CCS Associates ([contact]).

11.2.2.4 The DCP Medical Monitor and regulatory staff will determine which SAEs require FDA submission.

11.2.2.5 The Lead Organization and all Participating Organizations will comply with applicable regulatory requirements related to reporting SAEs to the IRB/IEC.

11.2.3 Follow-up of SAE

Site staff should send follow-up reports as requested when additional information is available. Additional information should be entered on the DCP SAE form in the appropriate format. Follow-up information should be sent to DCP as soon as available. SAEs related to study agent will be followed until resolution.

12. STUDY MONITORING

12.1 Data Management

All of the procedures outlined in the University of Wisconsin Chemoprevention Consortium standardized Data Management Plan (DMP approval 6/3/2013) will be followed in this protocol. There are no supplementary Data Management procedures for this protocol.

This study will report clinical data using the CLO database OnCore which is a web-based clinical trials/database. OnCore will be the database of record for the protocol and subject to NCI and FDA audit. All OnCore data entry will be performed at the CLO where staff is trained in OnCore per our DMP and applicable regulatory requirements such as 21 CFR; Part 11.

In order to standardize the collection of information, the CLO will provide POs with preprinted study-specific source documents.

12.2 Case Report Forms

Participant data will be collected using protocol-specific case report forms (CRF) developed from the standard set of DCP Chemoprevention CRF Templates and utilizing NCI-approved Common Data Elements (CDEs). The approved CRFs will be used to create the electronic CRF (eCRF) screens in OnCore. CLO staff will enter data into OnCore and transfer to Federal Security Compliant formats for transmission to DCP according to pre-established DCP standards and procedures. Amended CRFs will be submitted to the DCP Protocol Information Office for review and approval.

12.3 Source Documents

All data reported on CRFs must be documented on separate source documents found in the subject's medical record. The CLO will provide participating sites with standardized, pre-printed source documents that may be used to help ensure that all data items are collected. Participating sites are discouraged from using the CRFs for source documentation. If this practice occurs, the CRFs used as source documents must be signed and dated on the date of contact and a copy of the CRFs must be placed in the medical record as well as the research chart.

12.4 Data and Safety Monitoring Plan

The standard University of Wisconsin Chemoprevention Consortium DSMP was approved by the DCP on 9/14/2005. The UW Chemoprevention Consortium Data and Safety Monitoring Committee meet every 6-12 months to review all data from ongoing consortium studies. Members review pooled, unblinded safety data to assess ongoing human subjects safety.

12.5 Sponsor or FDA Monitoring

The NCI, DCP (or their designee), pharmaceutical collaborator (or their designee), or FDA may monitor/audit various aspects of the study. These monitors will be given access to facilities, databases, supplies and records to review and verify data pertinent to the study.

12.6 Record Retention

Clinical records for all participants, including CRFs, all source documentation (containing evidence to study eligibility, history and physical findings, laboratory data, results of consultations, *etc.*), as well as IRB records and other regulatory documentation will be retained by the Investigator in a secure storage facility in compliance with Health Insurance Portability and Accountability Act (HIPAA), Office of Human Research Protections (OHRP), Food and Drug Administration (FDA) regulations and guidances, and NCI/DCP requirements. The records for all studies performed under an IND will be maintained, at a minimum, for two years after the approval of a New Drug Application (NDA). For NCI/DCP, records will be retained for at least three years after the completion of the research. NCI will be notified prior to the planned destruction of any materials. The records will be accessible for inspection and copying by authorized persons of the Food and Drug Administration.

12.7 Cooperative Research and Development Agreement (CRADA)/Clinical Trials Agreement (CTA)

This section is not applicable for this study agent. The agent will be purchased by NCI.

12.7.1 Agent(s) may not be used for any purpose outside the scope of this protocol, nor can Agent(s) be transferred or licensed to any party not participating in the clinical study. Collaborator(s) data for Agent(s) are confidential and proprietary to Collaborator(s) and shall be maintained as such by the investigators. The protocol documents for studies utilizing investigational agents contain confidential information and should not be shared or distributed without the permission of the NCI. If a patient participating on the study or participant's family member requests a copy of this protocol, the individual should sign a confidentiality agreement. A suitable model agreement can be downloaded from the DCP website.

12.7.2 For a clinical protocol where there is an Investigational Agent used in combination with (an) other investigational Agent(s), each the subject of different collaborative agreements, the access to and use of data by each Collaborator shall be as follows (data pertaining to such combination use shall hereinafter be referred to as "Multi-party Data").

12.7.3 NCI must provide all Collaborators with prior written notice regarding the existence and nature of any agreements governing their collaboration with NIH, the design of the proposed combination protocol, and the existence of any obligations that would tend to restrict NCI's participation in the proposed combination protocol.

12.7.4 Each Collaborator shall agree to permit use of the Multi-Party Data from the clinical trial by any other Collaborator solely to the extent necessary to allow said other Collaborator to develop, obtain regulatory approval, or commercialize its own investigational agent.

12.7.5 Any Collaborator having the right to use the Multi-Party Data from these trials must agree in writing prior to the commencement of the trials that it will use the Multi-Party Data solely for development, regulatory approval, and commercialization of its own investigational agent.

12.7.6 Clinical Trial Data and Results and Raw Data developed under a collaborative agreement will be made available exclusively to Collaborator(s), the NCI, and the FDA, as appropriate. All data made available will comply with HIPAA regulations.

12.7.7 When a Collaborator wishes to initiate a data request, the request should first be sent to the NCI, who will then notify the appropriate investigators of Collaborator's wish to contact them.

12.7.8 Any manuscripts reporting the results of this clinical trial must be provided to DCP for immediate delivery to Collaborator(s) for advisory review and comment prior to submission for publication. Collaborator(s) will have 30 days (or as specified in the CTA) from the date of receipt for review. Collaborator shall have the right to request that publication be delayed for up to an additional 30 days in order to ensure that Collaborator's confidential and proprietary data, in addition to Collaborator(s)'s intellectual property rights, are protected. Copies of abstracts must be provided to DCP for forwarding to Collaborator(s) for courtesy review as soon as possible and preferably at least three days prior to submission, but in any case, prior to presentation at the meeting or publication in the proceedings. Press releases and other media presentations must also be forwarded to DCP prior to release. Copies of any manuscript, abstract, and/or press release/ media presentation should be sent to:

Head, DCP Protocol Information Office

E-mail: [contact]

The Protocol Information Office will forward manuscripts to the DCP Project Officer for distribution to the Collaborator(s). No publication, manuscript or other form of public disclosure shall contain any of Collaborator's confidential/proprietary information.

13. STATISTICAL CONSIDERATIONS

13.1 Study Design/Endpoints

This is a Phase IIa randomized, placebo-controlled, double-blind cancer chemoprevention trial of modulation of EGFR phosphorylation and other intermediate endpoint biomarkers by intermittent erlotinib in subjects with bladder cancer. Because there is a potential for a number of patients to be placed on a reduced dose of 300 mg/week because of intolerance to drug due to acne, in order to retain sufficient accrual at the 600 mg dose level, participants will be randomized in a 1:2 ratio of placebo to 600mg erlotinib administered weekly for 3 doses with the last dose approximately 24 hours of TURBT or cystectomy.

The primary endpoint for modulation of intermediate endpoint biomarkers will be the EGFR phosphorylation in normal appearing bladder epithelium adjacent to tumor 9-18 hours post-study dose; it is hypothesized that erlotinib will inhibit EGFR phosphorylation.

The secondary endpoints as prioritized include tolerance of high dose weekly erlotinib compared to placebo, EGF receptor phosphorylation in neoplastic bladder epithelium 9-18 hours post-study dose, the expression of e-cadherin and Ki67, the expression of phosphorylated ERK in normal and abnormal urothelium, limited pharmacokinetics of weekly erlotinib, the expression of p53 in normal and abnormal urothelium, and the expression of let-7 in normal and abnormal urothelium.

The primary analysis will be an as-randomized comparison of EGFR phosphorylation in bladder epithelium between the two randomized arms, based on two-sample t-test with normalizing transformation if necessary or Wilcoxon rank-sum test.

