6.8 Registration/Randomization

Participants will be considered registered on the trial when they sign the consent form. All patients who sign a consent form will be assigned a Participant Identification (PID) number. A set of unique sequential PID numbers will be provided to the PO in the form of a Study Registration Log. This log will be provided to the PO by the CLO at the study initiation.

Randomization

Participants will be randomized according to the scheme outlined in section 3. The study statisticians will provide the CLO with a stratified list of randomization numbers. The DCP Drug repository will also be provided with the list along with the treatment assignment that corresponds to each randomization number.

When an eligible participant is identified at the screening/baseline visit, the site will request randomization of the participant by faxing the appropriate documentation as outlined in the Study Visit Guides to the CLO at [contact].

The CLO will verify eligibility and confirm that the correct version of the informed consent was signed. Once this information is verified, the CLO will assign the next available randomization number from the stratification that applies to the participant (TURBT vs. cystectomy and use of agents which significantly decrease erlotinib bioavailability). The CLO will then fax an Investigational Agent Request form to the DCP drug repository requesting that the bottle of study agent corresponding to the randomization number

assigned the participant be shipped to the site's (investigational) pharmacy by overnight delivery. The site will follow local procedures to have the study agent dispensed to the participant once it is received at the pharmacy.

For next day delivery of study agent, the request for randomization must be received at the CLO office by 2:30 PM Eastern Time (1:30 PM Central Time) on the business day before the drug is needed. Per NCI policy, drug cannot be shipped on a Friday or the day before a holiday. There may be instances where a five-day turn-around is needed (holidays or unusual circumstances). If possible, please randomize a week before the drug is needed.

As soon as a subject has been randomized, the CLO will email a confirmation of randomization to the study coordinator at the PO. If a confirmation is not received within two hours, the coordinator should contact the CLO to confirm that randomization documents were received.

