13.2 Randomization and Stratification

Randomization will be in a ratio of 1:2 in Placebo (4 tablets): erlotinib (4 tablets) by mouth once weekly, based on a permuted block of size 3 with stratification by planned use of agents that significantly decrease Erlotinib bioavailability (tobacco, protein pump inhibitors) and by planned surgery (TURBT vs. cystectomy). The decision was made not to stratify by site to avoid problems with sparse data. After random permutation of numbers from 1 to 3 in each block, incoming subjects in sequence will be randomized to treatment corresponding to the permuted numbers in sequence according to the following: placebo for number 1, and erlotinib for numbers 2 and 3. This process will be repeated after every 3 subjects.

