13.3 Sample Size and Feasibility

The sample size for each group is based on comparing EGFR phosphorylation in bladder epithelium as measured by quantitative Vectra assay analysis of expression between the erlotinib and placebo arms. This primary endpoint can be considered a continuous random variable. The sample size justification is thus based on a two-tailed two-sample t-test of the difference between the two groups at a significance level of 0.05. In order to detect an effect size of 1, i.e. the difference in the mean change between the placebo arm and the erlotinib arm of 1 standard deviation, with power 0.85, the trial requires an effective sample size of 14 in the placebo arm and 28 in the erlotinib arm. Assuming a random drop-out of up to 5%, 15 subjects in the placebo arm and 30 subjects in the erlotinib arm will be enrolled for a total of 45 subjects for this exploratory study.

There will be six sites participating in the study. Each randomized patient will be treated with study medication weekly x 3 doses. We will allow for study duration of approximately 3 years.

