13.4 Primary Objective

The primary objective is to determine if there is a difference in EGFR phosphorylation in normal appearing bladder epithelium adjacent to tumor approximately 9-18 hours post-study dose, between patients randomized to erlotinib weekly as compared to placebo. The primary endpoint of the study is EGFR phosphorylation in bladder epithelium at the end of study (weekly for 3 doses) in subjects with bladder cancer. For the primary comparison the difference between the placebo group and the erlotinib group will be tested as-randomized using a two-sample t-test with normalizing transformation if necessary or Wilcoxon rank-sum test.

Because of the required dose modification to 300 mg for grade 2 rash or diarrhea and allowed dose modification for grade 1 rash/diarrhea if subject prefers (refer to section 5.6) there is the potential for a number of patients to reduce dose at some point in the study. In addition, prior research has shown that smokers and those that regularly take proton pump inhibitors metabolize erlotinib faster, tolerating

erlotinib better, but gaining fewer benefits, effectively receiving a reduced dose compared to non-smokers and those that are not taking proton pump inhibitors (refer to section 2). As a supporting analysis for the primary endpoint we will explore a relationship for EGFR phosphorylation with a measure of dose received, and accounting for smoking status and proton pump inhibitor use.

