13.8 Evaluation of Outcome/Endpoints

For the primary analysis comparing EGFR phosphorylation across the treatment groups, the as-randomized analysis will be used. All of the participants who met the eligibility criteria, with the exception of those who did not receive study agent, will be included in the main analysis. Random dropouts will be excluded.

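### Randomization is stratified by planned surgery and by smoking or proton pump inhibitor use, but the primary test adjusts for neither, which gives up some power.

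*Combined protocol and SAP*

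**What the plan says.** Section 13.2 randomizes 1:2 in permuted blocks of 3, "with stratification by planned use of agents that significantly decrease Erlotinib bioavailability" and also by TURBT versus cystectomy. Section 6.8 has the lead organization work from stratified lists: "the CLO will assign the next available randomization number from the stratification that applies to the participant". Both factors are therefore on record for every randomized participant before the first dose.

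The primary comparison appears in three places. Section 13.1 has it "based on two-sample t-test with normalizing transformation if necessary or Wilcoxon rank-sum test". Section 13.4 has it "tested as-randomized using a two-sample t-test with normalizing transformation if necessary or Wilcoxon rank-sum test". Section 13.8 adds no covariate: "For the primary analysis comparing EGFR phosphorylation across the treatment groups, the as-randomized analysis will be used".

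Section 13.4 also plans an exploratory supporting analysis against dose received, "accounting for smoking status and proton pump inhibitor use". Planned surgery is named in no analysis.

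On the choice of test, 13.3 states "This primary endpoint can be considered a continuous random variable" and continues "The sample size justification is thus based on a two-tailed two-sample t-test of the difference between the two groups". No section says when a transformation becomes necessary, which one it would be, or when the Wilcoxon test replaces the t-test.

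**The concern.** Stratified randomization balances the factors between arms, so part of the outcome variance no longer contributes to the difference in means. An unadjusted test still counts that variance in its standard error. If the factors predict the outcome, the standard error is too large, the test rejects less than 5% of the time under the null, and power is lost. The trial would have done the work of stratifying without taking the benefit. With 42 evaluable participants, a few points of power that need no extra participant are worth having.

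The open choice among three tests is a smaller matter. It leaves the primary p-value dependent on a decision that the plan does not tie down, and 6.9 lists the study statisticians among the unblinded personnel.

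**Working it through.** **Inputs from the documents (13.2, 13.3).** Two-sided alpha 0.05; effect 1 SD; 14 placebo and 28 erlotinib evaluable; power 0.85; drop-out up to 5%; blocks of 3; two binary stratification factors, hence four strata.

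**Assumed, because the documents do not give them.** R2, the share of within-arm outcome variance that the two factors explain (0, 0.1 and 0.2, split equally); 40% smoker/PPI; 30% cystectomy, with 20% as a check.

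**Step 1: the plan's own figure.** The noncentrality is 1 × sqrt(14 × 28 / 42) = sqrt(9.333) = 3.055, with 40 degrees of freedom and critical value 2.021. Power is 0.846, against the stated 0.85. For enrolment, 14/0.95 = 14.7 and 28/0.95 = 29.5, giving 15 and 30. The sample size reproduces.

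**Step 2: power of the adjusted model.** The residual SD becomes sqrt(1 − R2), so the noncentrality is 3.055 / sqrt(1 − R2). Two covariates leave 38 degrees of freedom (critical value 2.024).

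| R2 | Noncentrality | Power |
|---|---|---|
| 0 | 3.055 | 0.845 |
| 0.1 | 3.220 | 0.881 |
| 0.2 | 3.416 | 0.914 |

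**Step 3: the unadjusted test under stratified allocation.** With near-perfect balance the difference in means varies by a factor sqrt(1 − R2) less than its standard error implies, so the effective critical value is about 2.021 / sqrt(1 − R2). At R2 0.1 that is 2.130, a type I error of about 3.9%. At R2 0.2 it is 2.260, or about 2.9%.

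**Step 4: simulation of the actual design** (n = 42, blocks of 3 in four strata, 10,000 trials per scenario, normal data, 30% cystectomy).

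| R2 | Type I error, unadjusted | Type I error, adjusted | Power, unadjusted | Power, adjusted |
|---|---|---|---|---|
| 0 | 5.1% | 5.1% | 0.845 | 0.843 |
| 0.1 | 3.8% | 5.1% | 0.855 | 0.879 |
| 0.2 | 3.2% | 4.9% | 0.870 | 0.913 |

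With 20% cystectomy, power is 0.850 against 0.874 at R2 0.1 and 0.867 against 0.914 at R2 0.2. Separate reruns agree to within simulation error. The gain is 2.4 points at R2 0.1 and 4.3 to 4.7 points at R2 0.2. The cost at R2 0 is 0.2 points.

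**Step 5: smoking/PPI as an effect modifier only.** Section 5.5 gives reduced erlotinib exposure as the reason for stratifying on PPI use. If smoking/PPI halves the drug effect and does nothing else (average effect kept at 1 SD), power is 0.828 unadjusted and 0.837 adjusted, a gain of 0.9 points.

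**Step 6: the open choice of test.** With lognormal data (log-SD 1.0, strata not prognostic), unadjusted power is about 0.74 on the raw scale, 0.84-0.85 on logs and 0.81-0.83 for Wilcoxon, so the choice matters. If someone took the smallest of the three p-values, type I error with lognormal data (log-SD 0.6-1.0) would be 6.9-7.5% at R2 0, 5.8-6.1% at R2 0.1 and 4.4-4.8% at R2 0.2. With the strata in all three tests it would be 7.1-7.9% at every R2. Adjustment removes the conservatism that would otherwise mask the problem, so scale and adjustment belong in the same edit.

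**The case against.** The strongest reply is that nothing here is an error. The trial is sized and analysed with the same family of test, the sample size reproduces, and leaving out the strata cannot create a false positive. All of that stands.

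The second reply is that the gain rests on an R2 that the documents do not supply. That also stands. For smoking/PPI the stated mechanism is drug exposure, which can act only in the erlotinib arm, and there the gain is about 1 point. For surgery the support is indirect: 2.3 links EGFR overexpression to tumor grade and stage, and 2.1 says that muscle-invasive disease generally leads to cystectomy, but neither concerns phosphorylated EGFR in adjacent normal-appearing tissue. What keeps the point alive is the asymmetry: a possible gain of 2-5 points against a cost of a fraction of a point.

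The third reply is that 13.4 already accounts for smoking and PPI use. It does, but in an exploratory dose-relationship analysis that omits surgery and does not supply the primary p-value.

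On the choice of test, a reader might infer that the plan has no default at all. That goes too far. The t-test is named first, the transformation is conditional, and 13.3 sizes the trial on a t-test. What is missing is a selection rule. Nor do the documents propose picking the smallest p-value, so the figure of about 7% shows what the wording permits and does not predict what will be done.

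**Conclusion.** The point holds as one of efficiency. The primary test ignores both stratification factors, and planned surgery is used nowhere. Under an assumed R2 of 0.1 to 0.2 this gives up about 2-5 points of power and makes the test conservative (3.8% and 3.2% in place of 5%). The gain from adjusting is about 1 point if smoking/PPI is purely an effect modifier, and the cost is under 1 point if the strata do not matter. These sizes depend on the assumed R2, the assumed stratum shares and normal data.

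A reader might infer that the primary test is invalid or the trial underpowered. The documents support neither: the unadjusted test does not exceed its nominal level, and the stated power holds to within rounding (0.846). The missing selection rule is a real but secondary gap in pre-specification.

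**What to change.** In 13.1 and 13.4, make the primary analysis a linear model of phosphorylated EGFR in adjacent normal-appearing urothelium on arm, planned surgery and smoking/PPI use. Use main effects only, with the strata as recorded at randomization, and a two-sided 0.05 test of the arm term. Report the unadjusted t-test alongside.

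In the same edit, fix one scale for that model before assay results are merged with allocation. The raw scale is the one that 13.3 implies; if logs are preferred, say so in advance. Name regression of ranks on the same terms, or a stratified rank test, as the single sensitivity analysis.

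A data-driven sequence (a normality test, then logs, then ranks) is tempting but not advised. It helps with lognormal data of log-SD 1.0 (power about 0.83 against 0.74 on the raw scale). It can lose heavily if many values sit at the floor: with an assumed 30% or 50% exact zeros unaffected by drug, power was 0.30 against 0.46 and 0.13 against 0.28 for the plain t-test. Optical density may not give exact zeros, but 2.3 cites a series in which 78% of adjacent urothelium was negative for EGFR, so a floor is conceivable.

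The cost is wording and two degrees of freedom. No new data, visits or participants are needed. If the scale is to be settled after looking at pooled assay values, an analyst without the allocation list should do it, given 6.9.
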